17.2.1 LABORATORY SPECIFIC DERIVATIONS

- Homeostatic Model Assessment of Insulin Resistance (HOMA-IR) will be calculated for each visit:

$$\text{HOMA-IR} = \text{Glucose (mg/dL)} \times \text{Insulin (mU/L)} / 405$$

- The following conversion factors will be used if needed:

$$\text{Glucose (mg/dL)} = \text{Glucose (mmol/L)} \times 18.015588;$$

$$\text{Insulin (mU/L)} = \text{Insulin (pmol/L)} \times (1/6).$$

If both central and local lab results are available for a given assessment, preference should be given to the central lab result.

Document: CCI

Author: PPD

Version Number: 0.6

Version Date: 30JAN2023

Template No.: CS_TP_BS016 Revision 6

Reference: CS_WI_BS005

Effective Date: 02Dec2019

17.2.2 LABORATORY REFERENCE RANGES

Laboratory reference range indicators will be provided by the laboratory vendor and used in statistical analyses. Only if a reference range indicator is missing in the data transfer will it be derived in the analysis step as described below.

- Quantitative laboratory measurements (that are not urinalysis erythrocytes or urinalysis leukocytes) will be compared with the relevant laboratory reference ranges in original units and categorized as:
 - Low: Below the lower limit of the laboratory reference range.
 - Normal: Within the laboratory reference range (upper and lower limit included).
 - High: Above the upper limit of the laboratory reference range.
- For laboratory parameters with categorical outcomes, as well as urinalysis erythrocytes and urinalysis leukocytes, if the result is within the reference range, the indicator is “NORMAL”; if the result is not within range, the indicator is “ABNORMAL”.

17.2.3 DEFINITION OF METABOLIC IMPAIRMENT

Based on Alberti et al, metabolic impairment is defined as follows:

- If a male subject meets at least 3 out of 5 of the characteristics listed below, the subject is considered metabolically impaired at Baseline.
 - Baseline waist circumference \geq 102 cm
 - Baseline fasting triglycerides \geq 150 mg/dL (1.7 mmol/L) or use of drug treatment for elevated triglycerides at Baseline
 - Baseline fasting HDL $<$ 40 mg/dL (1.0 mmol/L) or use of drug treatment for reduced HDL at Baseline
 - (Baseline supine systolic blood pressure \geq 130 mmHg and/or Baseline supine diastolic blood pressure \geq 85 mmHg) or use of anti-hypertensive medications at Baseline
 - Baseline fasting glucose \geq 100 mg/dL or use of antidiabetic medications at Baseline

Document: **CCI** XXXXXXXXXX

Author: **PPD** XXXXXXXXXX

Version Number: 0.6

Version Date: 30JAN2023

Template No.: CS_TP_BS016 Revision 6

Reference: CS_WI_BS005

Effective Date: 02Dec2019

- If a female subject meets at least 3 out of 5 of the characteristics listed below, the subject is considered metabolically impaired at baseline.
 - Baseline waist circumference \geq 88 cm
 - Baseline fasting triglycerides \geq 150 mg/dL (1.7 mmol/L) or use of drug treatment for elevated triglycerides at Baseline
 - Baseline fasting HDL $<$ 50 mg/dL (1.3 mmol/L) or use of drug treatment for reduced HDL at Baseline
 - (Baseline supine systolic blood pressure \geq 130 mmHg and/or Baseline supine diastolic blood pressure \geq 85 mmHg) or use of anti-hypertensive medications at Baseline
 - Baseline fasting glucose \geq 100 mg/dL or use of antidiabetic medications at Baseline

The use of medications for elevated triglycerides or reduced HDL, anti-hypertensive medications, and antidiabetic medications at Baseline will be determined based on blinded data review prior to database lock. These medications must have started before study medication first dose and must have ended after study medication first dose or be ongoing to be considered as being used at Baseline.

17.3 ECG EVALUATIONS

Data from the centrally over-read ECG (Electrocardiogram) results will be included in the reporting of this study.

The following ECG parameters will be reported for this study:

- PR Interval (msec)
- RR Interval (msec)
- QRS Duration (msec)
- QRS Axis (deg)
- QT Interval (msec)
- QTcF Interval (msec) (Fridericia's Correction of QT interval)

Document: CCI

Author: PPD

Version Number: 0.6

Version Date: 30JAN2023

Template No.: CS_TP_BS016 Revision 6

Reference: CS_WI_BS005

Effective Date: 02Dec2019

- QTcB Interval (msec) (Bazett's Correction of QT interval)
- Heart Rate (bpm)
- Overall assessment of ECG as determined by the central over-read:
 - Normal
 - Abnormal, Insignificant
 - Abnormal, Potentially Significant
 - Abnormal, Significant
 - Not Evaluable
- ECG findings
 - ECG findings will only be listed. Other ECG data will be summarized in tables as well as presented in listings.
 - The following summaries will be provided:
- By-visit summary of observed values and change from Baseline values for quantitative measurements.
- By-visit summary of ECG overall assessment results as determined by the central over-read ("Normal", "Abnormal, Insignificant", "Abnormal, Potentially Significant", "Abnormal, Significant", "Not Evaluable").
- Shift in ECG overall assessment as determined by the central over-read from Baseline to Week 1/Visit 3, Week 4/Visit 5, Week 12/Visit 7, Week 24/Visit 10, Week 36/Visit 13, Week 52/Visit 17, and LOCF Endpoint.
- Number and percentage of subjects who met each of the QTc interval prolongation criteria (see [Section 17.3.1](#)). The period of evaluation includes both the double-blind treatment period and the follow-up period up to and including 9 days after the last dose of study drug, including unscheduled visits.
- Number and percentage of subjects with at least one PCS ECG value (see [Section 17.3.2](#)) post-

Document: **CCI**Author: **PPD**

Version Number: 0.6

Version Date: 30JAN2023

Template No.: CS_TP_BS016 Revision 6

Reference: CS_WI_BS005

Effective Date: 02Dec2019

Baseline. The period of evaluation includes both the double-blind treatment period and the follow-up period up to and including 9 days after the last dose of study drug, including unscheduled visits.

Subjects will be counted in a particular PCS category if they met that PCS criteria at least once during the period of evaluation, regardless of their Baseline value.

All ECG parameters, overall assessment as determined by the central over-read, and findings will be provided in a data listing. In addition, separate listings will be generated to present the QTc interval data of subjects who met at least one QTc prolongation criterion and the ECG data that met the PCS criteria.

17.3.1 QTc INTERVAL PROLONGATION CRITERIA

QTc interval prolongation will be identified in accordance with the following predefined criteria (same criteria apply to both QTcF and QTcB):

- >450 msec at any post-Baseline time point (including unscheduled visit) not present at Baseline
- >480 msec at any post-Baseline time point (including unscheduled visit) not present at Baseline
- >500 msec at any post-Baseline time point (including unscheduled visit) not present at Baseline
- ≥ 30 msec increase from Baseline for at least one post-Baseline measurement (including unscheduled visits) and < 60 msec increase from Baseline for all post-Baseline measurements (including unscheduled visits)
- ≥ 60 msec increase from Baseline for at least one post-Baseline measurement (including unscheduled visits)

17.3.2 ECG POTENTIALLY CLINICALLY SIGNIFICANT CRITERIA

Potentially clinically significant ECG measurements will be identified in accordance with the following predefined PCS criteria:

Table 3: Predefined ECG PCS criteria.

ECG Parameter	PCS Low	PCS High
---------------	---------	----------

Document:	CCI		
Author:	PPD	Version Number:	0.6
Template No.: CS_TP_BS016 Revision 6		Version Date: 30JAN2023	
Effective Date: 02Dec2019			Reference: CS_WI_BS005

Heart Rate (beats/min)	--	≥100
PR Interval (msec)	--	≥210
QRS Interval (msec)	--	≥120

17.4 VITAL SIGNS

The following Vital Signs measurements will be reported for this study:

- Supine and Standing SBP (mmHg)
- Supine and Standing DBP (mmHg)
- Supine and Standing Pulse Rate (bpm)
- Respiratory Rate (breaths/min)
- Temperature (°C)
- Weight (kg)
- BMI (kg/m²)
- Waist Circumference (cm)

The following summaries will be provided for vital signs data:

- By-visit summary of observed values and change from Baseline values for vital sign measurements, including Follow-up/Visit 18.
- Number and percentage of subjects with at least one PCS vital sign value (see [Section 17.4.2](#)) post-Baseline. The period of evaluation includes both the double-blind treatment period and the follow-up period up to and including 9 days after the last dose of study drug, including unscheduled visits. Subjects will be counted in a particular PCS category if they met that PCS criteria at least once during the period of evaluation, regardless of their Baseline value.
- Number and percentage of subjects with orthostatic hypotension and/or orthostatic tachycardia (see

Document: **CCI**

Author: **PPD**

Version Number: 0.6

Version Date: 30JAN2023

Template No.: CS_TP_BS016 Revision 6

Reference: CS_WI_BS005

Effective Date: 02Dec2019

Section 17.4.1). The data will be summarized for Baseline and the overall post-Baseline period (which covers both the double-blind treatment period and the follow-up period up to and including 9 days after the last dose of study drug, including unscheduled visits), as well as by visit, including Follow-up/Visit 18.

- By-visit summary of BMI category and shift in BMI category from Baseline to each post-Baseline time point. BMI categories are listed in Section 7.5.
- By-visit summary of observed values and change from Baseline values for vital signs measurements by BMI category.
- The change from Baseline values at Week 52/Visit 17 and LOCF Endpoint for weight and BMI will be analyzed using nonparametric rank ANCOVA similarly to the analysis described in Section 17.2.
- By-visit summary and PCS summary based on metabolically impaired subjects at baseline (see Section 17.2.3) and non-metabolically impaired subjects at baseline.

All vital signs data will be provided in a data listing. In addition, a separate listing will be generated to present the vital signs data that met the PCS criteria. All occurrences of orthostatic hypotension and orthostatic tachycardia will also be presented in a listing.

A boxplot will be created to present weight data by time point and treatment group for all subjects, for the subset of subjects who are metabolically impaired at Baseline, and for the subset of subjects who are non-metabolically impaired at baseline. The boxplots will be repeated to present the change from Baseline values.

17.4.1 VITAL SIGNS SPECIFIC DERIVATIONS

- BMI expressed in kg/m² = Weight (kg)/ height (m)².

The height collected at Visit 1 will be used to derive BMI where needed throughout the study.

- Orthostatic hypotension is defined as a decrease of ≥ 20 mmHg in SBP or ≥ 10 mmHg in DBP after a subject has been standing for at least 2 to 4 minutes, compared to the SBP and DBP in the supine position, respectively.
- Orthostatic tachycardia is defined as a heart rate increase of ≥ 20 bpm after a subject has been

Document: CCI

Author: PPD

Version Number: 0.6

Version Date: 30JAN2023

Template No.: CS_TP_BS016 Revision 6

Reference: CS_WI_BS005

Effective Date: 02Dec2019

standing for at least 2 to 4 minutes compared to the heart rate measured in the supine position, and a heart rate of >100 bpm after the subject has been standing for at least 2 to 4 minutes.

17.4.2 VITAL SIGNS POTENTIALLY CLINICALLY SIGNIFICANT CRITERIA

Potentially clinically significant vital sign measurements will be identified in accordance with the following predefined PCS criteria:

Table 4: Predefined vital sign PCS criteria.

Vital Sign Parameter	PCS Low	PCS High
SBP (Supine, Standing) (mmHg)	Value \leq 90 and \geq 20 decrease from Baseline	Value \geq 180 and \geq 20 increase from Baseline
DBP (Supine, Standing) (mmHg)	Value \leq 50 and \geq 15 decrease from Baseline	Value \geq 105 and \geq 15 increase from Baseline
Pulse Rate (Supine, Standing) (beats/min)	Value \leq 50 and \geq 15 decrease from Baseline	Value \geq 120 and \geq 15 increase from Baseline
Weight (kg)	\geq 7% decrease from Baseline	\geq 7% increase from Baseline
Temperature (°C)	NA	Value \geq 38.3°C and \geq 0.8°C increase from Baseline

17.5 PHYSICAL EXAMINATION

As all physical and neurological findings will be recorded as medical history or AEs, no specific analysis of physical and neurological examination will be performed.

Document: CCI

Author: PPD

Version Number: 0.6

Version Date: 30JAN2023

Template No.: CS_TP_BS016 Revision 6

Reference: CS_WI_BS005

Effective Date: 02Dec2019

17.6 OTHER SAFETY ASSESSMENTS

17.6.1 COLUMBIA SUICIDE SEVERITY RATING SCALE (C-SSRS)

The C-SSRS is a tool designed to systematically assess and track suicidal behavior and suicidal ideation for life time, one month prior to the screening visit for suicidal ideation and 6 months prior to the screening visit for suicidal behavior, and throughout the study. The strength of this suicide classification system is in its ability to comprehensively identify suicidal events while limiting the over-identification of suicidal behavior. The C-SSRS Baseline/Screening Version is used at the screening visit and the C-SSRS Since Last Visit Version is used from Visit 2 and onward. Subjects with Type 4 (active suicidal ideation with some intent to act, without specific plan) or Type 5 (active suicidal ideation with specific plan and intent) suicidal ideation during the study will be discontinued from the study and referred to a mental health professional.

C-SSRS includes two main sections: Suicidal Ideation and Suicidal Behavior.

The following outcomes are C-SSRS categories and have binary responses (yes/no). The categories are re-ordered from the scale to facilitate the definitions of the C-SSRS endpoints, and to provide clarity in the presentation of the results.

- Suicidal ideation is measured by 5 categories, representing 5 subtypes of suicidal ideation with increasing severity:
 - Category 1: Wish to be Dead
 - Category 2: Non-specific Active Suicidal Thoughts
 - Category 3: Active Suicidal Ideation with Any Methods (Not Plan) without Intent to Act
 - Category 4: Active Suicidal Ideation with Some Intent to Act, without Specific Plan
 - Category 5: Active Suicidal Ideation with Specific Plan and Intent
- Suicidal behavior is measured by 5 categories, representing 5 subtypes of suicidal behavior:
 - Category 6: Preparatory Acts or Behavior
 - Category 7: Aborted Attempt

Document: CCI

Author: PPD

Version Number: 0.6

Version Date: 30JAN2023

Template No.: CS_TP_BS016 Revision 6

Reference: CS_WI_BS005

Effective Date: 02Dec2019

- Category 8: Interrupted Attempt
- Category 9: Actual Attempt (non-fatal)
- Category 10: Completed Suicide

The 10 categories above are not mutually exclusive. Subjects will be counted in each category for which they have an event.

Self-injurious behavior without suicidal intent is a non-suicide-related C-SSRS outcome, and also has a binary response (yes/no).

For the purpose of C-SSRS analysis, “Baseline” and the overall “post-Baseline” period are defined as follows.

Time point	Study Visit	C-SSRS Version	Derivation Rule
Baseline	Visit 1	Baseline/Screening – Past 1 Month for Suicidal Ideation / Past 6 Months for Suicidal Behavior	Most severe outcome
	Visit 2*	Since Last Visit	
Post-Baseline	All post-Baseline visits up to and including 9 days after the last dose of study drug, including unscheduled visits	Since Last Visit	Most severe outcome

* Note: The Visit 2 C-SSRS assessment must be administered prior to the first dose of study medication in order to be used in the C-SSRS Baseline derivation.

The following C-SSRS composite endpoints will be derived for each time point of interest (i.e. Baseline, overall post-Baseline, and each scheduled visit including Follow-up/Visit 18) as follows:

- Any suicidal ideation: A “yes” answer to any one of the 5 suicidal ideation questions on C-SSRS (Categories 1 to 5).
- Any suicidal behavior: A “yes” answer to any one of the 5 suicidal behavior questions on the C-SSRS (Categories 6 to 10).

Document: CCI

Author: PPD

Version Number: 0.6

Version Date: 30JAN2023

Template No.: CS_TP_BS016 Revision 6

Reference: CS_WI_BS005

Effective Date: 02Dec2019

- Any suicidality: A “yes” answer to any one of the 10 suicidal ideation and behavior questions on the C-SSRS (Categories 1-10).

For each subject, the suicidal ideation score at each time point of interest (i.e. Baseline, overall post-Baseline, the LOCF endpoint, and each scheduled visit including Follow-up/Visit 18) is defined as the maximum suicidal ideation category (1-5) present for the time point of interest. If no ideation is present a score of 0 is assigned.

The number and percentage of subjects with any suicidality, any suicidal ideation and subtypes of ideation, any suicidal behavior and subtype of behavior, and any non-suicidal self-injurious behavior will be presented for:

- Baseline (as defined above)
- The overall post-Baseline period (as defined above)
- Each scheduled visit: Screening/Visit 1 (lifetime; past 1 month for ideation/past 6 months for behavior), Randomization/Visit 2, Week 1/Visit 3, Week 2/Visit 4, Week 4/Visit 5, Week 8/Visit 6, Week 12/Visit 7, Week 16/Visit 8, Week 20/Visit 9, Week 24/Visit 10, Week 28/Visit 11, Week 32/Visit 12, Week 36/Visit 13, Week 40/Visit 14, Week 44/Visit 15, Week 48/Visit 16, Week 52/Visit 17, and Follow-up/Visit 18.

Difference between SEP-363856 50 to 100 mg/day treatment group against the Quetiapine XR 400 to 800 mg/day group for the proportion of subjects with any suicidality, any suicidal behavior, and any suicidal ideation at Baseline and during the overall post-Baseline period will be evaluated using Fisher's Exact test.

Shift in suicidal ideation score from Baseline to the overall post-Baseline period, to each of the scheduled visits (Week 1/Visit 3, Week 2/Visit 4, Week 4/Visit 5, Week 8/Visit 6, Week 12/Visit 7, Week 16/Visit 8, Week 20/Visit 9, Week 24/Visit 10, Week 28/Visit 11, Week 32/Visit 12, Week 36/Visit 13, Week 40/Visit 14, Week 44/Visit 15, Week 48/Visit 16, Week 52/Visit 17, and Follow-up/Visit 18), and to the LOCF endpoint will be presented.

Intensity of ideation for the most severe ideation subtype is measured in terms of frequency, duration, controllability, deterrents, and reasons for ideation. Each is measured with responses ranging from 1 to 5 for frequency and duration, and from 0 to 5 for controllability, deterrents, and reasons for ideation. The ideation intensity total score is the sum of responses to the five items and can range from 2 to 25 for

Document: CCI

Author: PPD

Version Number: 0.6

Version Date: 30JAN2023

Template No.: CS_TP_BS016 Revision 6

Reference: CS_WI_BS005

Effective Date: 02Dec2019

subjects with endorsed suicidal ideation. For subjects with endorsed suicidal ideation, if one or more of these five items are missing at an assessment, the total score will be set to missing. If a subject did not endorse any suicidal ideation, a score of 0 for the ideation intensity total score will be given.

Actual lethality associated with actual attempts is rated on a 6-point scale from 0 = 'No physical damage or very minor physical damage' to 5 = 'Death'. Potential lethality of actual attempts (if actual lethality = 0) is rated on a 3-point scale from 0 = 'Behavior not likely to result in injury' to 2 = 'Behavior likely to result in death despite available medical care'.

Responses to each C-SSRS question will be listed. The ideation intensity total score and the actual lethality and potential lethality of actual attempts will only be presented in data listings.

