15.3.6.7. Suicidality Measure

Frequency and severity of suicidal ideation and suicidal behavior as measured by the C-SSRS scale will be summarized by treatment for the overall post-Baseline period and by visit.

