If the event date is due to the fourth criterion and is beyond Study Day 364, it will be re-set to the date of Study Day 364. If the event date is due to one of the other three relapse criteria and is beyond Study Day 365, it will be re-set to the date of Study Day 365. A censoring date that is beyond Study Day 365 will be re-set to the date of Study Day 365.

Kaplan-Meier estimates of the median time-to-relapse and the 25th percentile and 75th percentile of time-to-relapse, along with the respective 95% confidence intervals, will be calculated. Kaplan-Meier estimate of the probability of relapse at the end of the treatment period, and its 95% confidence interval, will also be calculated. The time-to-relapse data will be presented in a Kaplan-Meier curve along with log rank test statistic. The log rank test will be used to compare the time-to-relapse (in days) between SEP-363856 50 to 100 mg/day and Quetiapine XR 400 to 800 mg/day treatment groups.

The rate of relapse will be calculated as the proportion of subjects demonstrating a relapse during the 52-week period treatment period out of the EFF population. The 95% confidence interval for the rate of relapse will also be calculated.

The frequency of hospitalizations due to relapse will be summarized by treatment group.

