17.1.11 ADVERSE EVENTS EXPLORATORY ANALYSIS

Odds ratios (OR) with 95% CIs and p-values will be provided for all AEs, SAEs, AEs leading to

Document: **CCI**

Author: **PPD**

Version Number: 0.6

Version Date: 30JAN2023

Template No.: CS_TP_BS016 Revision 6

Reference: CS_WI_BS005

Effective Date: 02Dec2019

discontinuation, and AEs relating to extrapyramidal symptoms (EPS) between the two treatment groups using a logistic regression model with treatment and geographic region as categorical factors.

Each subject will be counted only once for each AE type. Categories for each treatment group will be AE vs no AE for each AE type listed above.

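### Suicidality and time to relapse are tested against quetiapine XR with no planned between-arm estimate or confidence interval, so a non-significant result carries no planned bound on excess risk

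*SAP*

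**What the plan says.** **Suicidality.** Protocol 15.3.6.7 plans a descriptive analysis: "Frequency and severity of suicidal ideation and suicidal behavior as measured by the C-SSRS scale will be summarized by treatment". SAP 17.6.1 tabulates by arm "The number and percentage of subjects with any suicidality, any suicidal ideation and subtypes of ideation", and likewise for behavior and non-suicidal self-injury. It then adds a test. For the three composites of suicidality, behavior and ideation, differences between the arms "during the overall post-Baseline period will be evaluated using Fisher's Exact test", and Baseline is tested the same way. It names no risk difference, ratio or interval.

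**Relapse.** SAP 16.2.12 states: "The log rank test will be used to compare the time-to-relapse (in days) between SEP-363856 50 to 100 mg/day and Quetiapine XR". It also plans the median and quartiles of time to relapse with 95% CIs. On the end-of-treatment probability it says "Kaplan-Meier estimate of the probability of relapse at the end of the treatment period, and its 95% confidence interval, will also be calculated", and on the simple proportion relapsing it says "The 95% confidence interval for the rate of relapse will also be calculated". Since efficacy tables have one column per arm (SAP 16), these intervals describe each arm separately. No hazard ratio or difference between arms is named.

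**Elsewhere in the same SAP.** Section 17.1.11 says "Odds ratios (OR) with 95% CIs and p-values will be provided" for all AEs, SAEs, AEs leading to discontinuation and extrapyramidal AEs. Section 16.1.1.1 gives LS mean differences with 95% CIs for PANSS. Section 6.6 sets the default levels (5% two-sided tests, 95% intervals) but does not require an interval with every test.

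**The concern.** Suicidality is a named safety objective (Protocol 5.2) and maintenance of effect, including relapse, a named efficacy objective (Protocol 5.3). The comparator is active, no margin is defined, and the sample size rests on clinical considerations rather than power (Protocol 15.1, SAP 3.4). In that setting a p-value above 0.05 says little, because it may mean that the arms are alike or that there were too few events to tell. An interval separates these two cases. The SAP adds a significance test to a descriptive protocol analysis without adding the estimate needed to interpret it, so any choice of bound would be made after unblinding. What is at stake is whether the report can say how large an excess of suicidality, or how much worse relapse prevention, the data leave open.

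**Working it through.** **Inputs.** 300 subjects allocated 2:1 (Protocol 15.1) give 300 × 2/3 = 200 on SEP-363856 and 100 on quetiapine XR. Tests are two-sided at 5% (SAP 6.6) with no multiplicity adjustment (SAP 7.4). The documents give neither a suicidality rate nor an expected number of relapses, so both are assumptions and are shown as ranges.

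**The plan's own figure.** The only sample-size figure is about 80 one-year completers on SEP-363856, which implies 80/200 = 40% completion. No retention rate or power is stated, so there is no power figure to reproduce.

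**Fisher's test.** Exact power = Σ over all tables of Bin(a; 200, p_SEP) × Bin(b; 100, p_QXR) × I[Fisher p(a,b) ≤ 0.05]. Setting p_SEP = p_QXR gives the true size.

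| Assumed quetiapine XR rate | True size | Power, doubling | Power, tripling |
|---|---|---|---|
| 1% | 1.7% | 1% | 6% |
| 2% | 2.8% | 7% | 27% |
| 3% | 3.2% | 14% | 46% |
| 5% | 3.6% | 27% | 75% |
| 8% | 3.9% | 47% | 95% |
| 10% | 3.9% | 59% | 99% |

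Solving for 50% power gives a quetiapine XR rate of about 8.5% for a doubling and about 3.2% for a tripling.

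**What an interval would add.** SEP-363856 minus quetiapine XR:
- 6/200 vs 1/100: 3.0% - 1.0% = +2.0 points; Fisher p=0.43; Miettinen-Nurminen 95% CI -2.6 to +5.6 points.
- 4/200 vs 2/100: difference 0; p=1.00; Newcombe 95% CI -5.1 to +3.4 points.
- 8/200 vs 2/100: +2.0 points; p=0.51; Newcombe 95% CI -3.4 to +6.0 points.
- 20/200 vs 5/100: +5.0 points; p=0.18; Newcombe 95% CI -2.1 to +10.7 points.

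I recomputed the last three with Miettinen-Nurminen limits, and they differ by at most 0.2 points. Even with identical observed rates and p=1.00, an excess of over 3 points stays open, and the planned output would not show it.

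**Relapse.** With d events and 2:1 allocation, SE(ln HR) ≈ 1/√(d × 1/3 × 2/3) = 1/√(2d/9), and power ≈ Φ(ln HR / SE - 1.96).
- d=60, HR 1.5: SE = 1/√13.33 = 0.274; 0.405/0.274 - 1.96 = -0.48; power 32%.
- HR 1.5 with 40 and 90 events: 23% and 44%. HR 2.0 with 30, 60 and 90 events: 43%, 72% and 87%.
- d=75, observed HR 1.0: SE = 1/√16.67 = 0.245; 95% CI exp(±1.96 × 0.245) = 0.62 to 1.62.

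These calculations treat all 300 subjects as analysed. Shorter exposure through early discontinuation would reduce the number of events and lower the power.

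**The case against.** The strongest reply is that this is a safety study with no comparative hypothesis for suicidality. The protocol plans only a descriptive C-SSRS analysis. Of the safety objectives in Protocol 5.2, only the one on prolactin, metabolic measures, weight and BMI is framed as a comparison with quetiapine XR. Protocol 15.3.5 calls all efficacy analyses exploratory, and that covers relapse. Low power for a test the trial was not sized for is not an error. Counts by arm are tabulated, so a reader could work out an interval; relapse has per-arm intervals; and serious suicidal events count among the SAEs, which get an odds ratio with a CI. Output templates (SAP 8) are not in the public documents and may contain more.

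Most of this stands and limits the point. It does not remove it: once a between-arm test is planned, its estimate and interval belong beside it, as in 17.1.11, and leaving readers to derive them is not a plan.

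A reader might go further in three ways that the documents do not support:
- **That a doubling or tripling of suicidality would mostly be missed, whatever the rate.** At a 5% quetiapine XR rate a tripling is detected about 75% of the time. Entry excludes Item 4-5 ideation and suicide attempts within 6 months (Protocol 8.2), which makes low rates plausible for behavior. It does not exclude ideation Categories 1-3, which count towards any ideation and any suicidality.
- **That the plan would read non-significance as evidence of safety.** Neither document says so.
- **That Fisher's test is the wrong test.** It is conservative here, but it is a defensible choice for sparse counts. A mid-p version is a matter of preference; at a 1% rate its true size is the same 1.7%.

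**Conclusion.** The point holds as a reporting gap. For the three post-Baseline C-SSRS composites and for time to relapse, the SAP plans a between-arm test but no between-arm estimate or interval, so a null result has no planned bound on excess risk. Its weight depends on event rates that the documents do not give. With 200 versus 100 subjects, Fisher's test misses a doubling more often than not below a quetiapine XR rate of about 8.5%, and a tripling only below about 3.2%. The point is therefore most secure for suicidal behavior and weaker for any ideation or any suicidality, which may be commoner. The suicidality power figures do not carry over to relapse. There the gap is the missing hazard ratio, and its precision depends on an assumed event count. Nothing here shows that the trial is too small for its stated purpose.

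**What to change.** In SAP 17.6.1, keep Fisher's test and add, for each of the three post-Baseline composites, the SEP-363856 minus quetiapine XR risk difference with a Miettinen-Nurminen 95% CI.

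In SAP 16.2.12, add two exploratory estimates beside the log-rank test: a Cox hazard ratio (SEP-363856 vs quetiapine XR) with 95% CI, and the difference between arms in end-of-treatment Kaplan-Meier relapse probability with 95% CI.

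This needs no new data, takes a few lines of SAP text and code, and changes no clinical rule. The downside is presentational: with few events the intervals will be wide, and the stated uncertainty will look less favourable than a bare non-significant p-value.
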